#### 3.5 Data Collection

On attendance for colonoscopy and following completion of a written consent form, the participant will be asked to complete a health questionnaire. This can be done either by the participant alone or with help from a member of the research team. This questionnaire will include the following details:

- 1. Age
- 2. Ethnicity
- 3. Gender

- 4. Smoking History- current and previous
- 5. Alcohol consumption- current and previous
- 6. Medication history
- 7. Family history of colorectal cancer
- 8. Family history of ischaemic heart disease
- 9. History of liver disease
- 10. Hypertension history
- 11. Diabetic history
- 12. History of chronic kidney disease (stage 4/5, eGFR <30ml/min)
- 13. History of atrial fibrillation
- 14. History of rheumatoid arthritis
- 15. Previous anti-obesity surgery

The clinical notes will be used to confirm the indication for the colonoscopy and to support the health questionnaire where participants are unsure of details. The research nurse will measure blood pressure, weight, height, waist circumference and calculate the body mass index (BMI in kg/m^2). This information, including the health questionnaire, will be entered onto the case report form (CRF).

Blood tests will be taken to identify patients with fatty liver defined as:

- Definite if patients have raised ALT levels (above the upper limit of normal) and are overweight or obese (in the absence of excessive alcohol consumption)
- Probable if the ALT >30 IU/ml for males and >19 IU/ml for females and they are overweight or obese (in the absence of excessive alcohol consumption)

We will also determine stage of fibrosis defined by FIB-4 score ((age x AST)/(platelets x (VALT)) as:

- No / mild: FIB-4 score <1.3
- Moderate: FIB-4 score 1.3 2.67
- Advanced: FIB-4 score >2.67

We will also determine the patient's Qrisk 2 score and Fatty Liver Index (FLI) Score.

Patients undergoing a colonoscopy usually have an intravenous cannula inserted to allow administration of sedative medication, analgesia and smooth muscle relaxants. Where possible the blood tests will be taken at the time of cannula insertion. To enable this, a size 18G (green) cannula will be used. Where obtaining bloods from the cannula is not possible (failed attempt or poor venous access), this will be done using separate standard venepuncture methods. Blood samples will be collected in the appropriate containers and sent to the clinical laboratory at the site hospital. The blood tests will be requested and labelled according to individual site-specific usual practice. The samples will not be anonymised, to enable the results to be later checked by a research nurse and entered onto the pseudonymised CRF. The samples will be destroyed in line with individual site Trust policy (usually within 3-7 days). Bloods will include:

- 1. Bilirubin
- 2. Alanine aminotransferase (ALT)
- 3. Alkaline phosphatase (ALP)
- 4. Aspartate aminotransferase (AST)
- 5. Gamma-glutamyl transferase (GGT)
- 6. Immunoglobulin A
- 7. Full blood count (FBC)
- 8. HbA1c
- 9. Fasting blood glucose
- 10. Lipids: Cholesterol, HDL and Triglycerides
- 11. Albumin

In the event that haemolysis of LFTs occurs, patients will still be included in the study to allow for analysis of other risk factors and their association with adenomas.

Following colonoscopy to allow completion of the histological dataset, additional information will be collected either at the time of colonoscopy or from hospital reporting systems or from the patient record on the BCSP dataset. These will include:

- 1. Site and number of cancers diagnosed
- 2. Number of adenomas
  - a. Site
  - b. Morphology
  - c. Size
  - d. Villous component
  - e. Degree of dysplasia

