Obesity is increasingly prevalent in the UK, with 24.4% of men and 25.2% of women classed as obese in England. In addition to type II diabetes mellitus and increased cardiovascular risk, obesity is independently linked with increased colorectal neoplasia and recurrence of colorectal adenomas. One large European study found that up to 94% of obese individuals had non-alcoholic fatty liver disease (NAFLD), compared with 67% of overweight and 25% of normal weight patients. NAFLD is defined as fatty infiltration of the liver affecting more than 5% of hepatocytes, in the absence of alcohol excess or the consumption of steatogenic drugs. NAFLD encompasses various stages of fatty liver disease ranging from steatosis to steatohepatitis (fat + hepatocellular injury +/- fibrosis) through to cirrhosis and hepatocellular carcinoma. Obesity and type II diabetes are major risk factors for the progressive form of fatty liver, non-alcoholic steatohepatitis (NASH). At present there is no gold standard tool in screening for patients at risk of fatty liver disease, apart from identifying risk factors as mentioned above. The fatty liver index (FLI) is one such tool which incorporates height, weight, waist circumference, serum gamma-glutamyl transferase (GGT) and serum triglycerides, and if identified at high risk these patients be considered for further assessment for fatty liver with blood tests and ultrasonography. Approximately 40% of patients with NAFLD develop progressive fibrosis that can result in cirrhosis, putting patients at risk of hepatocellular carcinoma, liver failure and portal hypertension related complications. The development of advanced fibrosis (stage 3-4) in patients with NAFLD is clinically important as it is associated with a >3 fold increase risk of mortality (all-cause and liver-related) compared with a reference population. Non-invasive fibrosis scores, such as the FIB-4 score (comprising age, Aspartate aminotransferase (AST), Alanine aminotransferase (ALT) and platelet count), are reliable in diagnosing or excluding advanced fibrosis in patients with NASH and are

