#### 3.3 Exclusion Criteria

- 1. Absolute contraindication to colonoscopy
- 2. Unable to give informed consent
- 3. Known colorectal cancer
- 4. Known polyposis syndrome
- 5. Previous total/subtotal colectomy
- 6. Known colonic stricture which would prevent completion of colonoscopy
- 7. Attending for therapeutic procedure
- 8. Attending for assessment of a known lesion
- 9. Attending for assessment of known inflammatory bowel disease (IBD)
- Attending for surveillance colonoscopy (polyp surveillance, post colorectal cancer surveillance, IBD surveillance)
- 11. Colonoscopy within the last 5 years

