#### 6. Statistics and Data Analysis

Data from the CRFs will be transferred to a secure and encrypted electronic computer database. Statistical analysis will be undertaken by [name], Professor of Biological Modelling at Newcastle University.

The relationship between adenoma incidence, NAFLD and blood markers will be investigated using logistic regression whilst adjusting for patient-related demographic variables including age and gender. This will assess the independent contribution of predictors to the odds of adenomas being found. Stepwise removal of non-significant covariates will then be used to identify variables best able to predict adenoma presence. ROC plot and AUC analyses of sensitivity and specificity will be used to characterise the ability of the model to discriminate between patients with and without adenomas and their potential as a predictive tool. These analyses assess the independent contribution of variables to the probability that adenomas will be found, but do not allow for confounding, interaction and associated indirect effects on detection. Structural Equation Modelling (SEM) will be used to investigate impact of indirect and direct effects of the predictors on adenoma incidence. Parsimonious models for logistic regression and SEM will be compared in terms of their ability to predict adenoma presence.

As multiple adenomas may occur, the extent to which adenoma number is related to abnormal liver enzymes using Poisson regression models and SEM will be measured, following the same analytical framework. It is anticipated that the presence of multiple adenomas will be zero-inflated, with some patients having zero and others many. The extent to which zero-inflated models (eg allowing for aggregation) improve the prediction of adenomas will be assessed. Robustness and validation of all models will be validated using bootstrapping. The best model will be developed into a predictive tool.

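### The fatty liver rule in Section 3.5 drops the steatogenic-drug exclusion of the protocol's own NAFLD definition, and could also use the liver disease history already collected

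*Protocol*

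**What the plan says.** Section 1 of the protocol (Background) gives the disease definition: fat in more than a stated share of liver cells, "in the absence of alcohol excess or the consumption of steatogenic drugs".

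Section 3.5 (Data Collection) gives the classification rule, in two tiers:

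- The definite tier takes participants whose ALT is over the normal range and who "are overweight or obese (in the absence of excessive alcohol consumption").
- The second tier lowers the ALT threshold and sets it by sex: "Probable if the ALT >30 IU/ml for males and >19 IU/ml for females and they are overweight or obese". The same alcohol condition applies.

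Alcohol is the only exclusion in either tier. The questionnaire in the same section collects "Medication history" (item 6) and "History of liver disease" (item 9), but no sentence links either item to the classification.

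Section 6 makes NAFLD a predictor: "The relationship between adenoma incidence, NAFLD and blood markers will be investigated using logistic regression". Section 2.1 names NAFLD in primary objective 1.

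**The concern.** The case rule is looser than the definition it is meant to put into practice. Taken literally, an overweight participant without alcohol excess whose ALT is raised by a steatogenic drug is definite fatty liver under Section 3.5 and not NAFLD under Section 1. The same participant cannot be both.

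A second gap is of a different kind. Someone with another known liver condition is also classed as definite if overweight, with raised ALT and no alcohol excess. Section 1 does not list other liver disease as an exclusion, so this does not conflict with the text. It is information that the study gathers and the rule leaves unused.

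At stake is the NAFLD coefficient. If the wrongly included patients have no excess adenoma risk, the association is diluted. If the drugs or conditions themselves relate to adenoma risk, the bias can go in either direction.

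**Working it through.** **1. The texts side by side**

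| Condition | Section 1 | Section 3.5 |
|---|---|---|
| No alcohol excess | required | required, both tiers |
| No steatogenic drug | required | absent |
| No other known liver disease | not stated | absent |

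**2. Does anything else remove these patients?**

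- The exclusion criteria in Section 3.3 begin with "Absolute contraindication to colonoscopy" and run to 11 items. All concern the colon, the procedure or consent.
- The withdrawal criteria in Section 3.4 cover polyposis, incomplete procedures and withdrawn consent.
- The blood panel in Section 3.5 has no test for a specific alternative liver disease such as viral hepatitis.
- FIB-4 and the Fatty Liver Index, as described in Section 1, are built from age, body measures, enzymes, platelets and triglycerides. They cannot tell one cause of raised ALT from another.
- Fibroscan measures stiffness, and only in a subset.
- Covariate adjustment in Section 6 does not relabel a wrongly labelled case.

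So the rule in Section 3.5 decides.

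**3. The protocol's own figures (Section 3.1)**

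- N = 10k/p with k = 15 gives 150/0.15 = 1000 and 150/0.35 = 428.6, against the stated 1000 and 430.
- Detectable effect: β = √8 × 0.125 = 0.3536, and exp(0.3536) = 1.424, against the stated 1.42.

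Both reproduce. The finding depends on neither; 1.42 serves below only as a benchmark.

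**4. Illustration of dilution (assumed inputs)**

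Assumptions: reference adenoma risk p0 = 0.20; true OR 1.42; a share f of the labelled group has another cause of raised ALT and risk p0. The protocol's recruitment mix gives a similar reference risk: (0.15 × 1000 + 0.35 × 430)/1430 = 0.21, which yields the same ORs to two decimals.

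- Odds in true cases: 0.25 × 1.42 = 0.355, so p1 = 0.355/1.355 = 0.262.
- Risk in the labelled group: pm = (1 − f)·p1 + f·p0.
- Observed OR = [pm/(1 − pm)]/0.25.

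| f | pm | Observed OR |
|---|---|---|
| 5% | 0.2589 | 1.397 |
| 10% | 0.2558 | 1.375 |
| 20% | 0.2496 | 1.330 |

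**5. Net sample-size penalty against the repaired rule**

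The repair removes the dilution but also shrinks the exposed group, so both effects belong in the comparison. Let e be the share labelled under the current rule, here assumed to be 20%. For an unadjusted comparison the required N is proportional to:

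- current rule: [1/(e·pm(1 − pm)) + 1/((1 − e)·p0(1 − p0))] / (ln observed OR)²
- repaired rule: [1/(e(1 − f)·p1(1 − p1)) + 1/((1 − e)·p0(1 − p0))] / (ln 1.42)²

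| f | Current rule | Repaired rule | Ratio |
|---|---|---|---|
| 5% | (26.06 + 7.81)/(ln 1.397)² = 302.6 | (27.22 + 7.81)/(ln 1.42)² = 284.9 | 1.06 |
| 10% | 336.3 | 297.2 | 1.13 |
| 20% | (26.70 + 7.81)/(ln 1.330)² = 423.3 | (32.32 + 7.81)/(ln 1.42)² = 326.4 | 1.30 |

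With e between 10% and 40%, the penalty at f = 20% runs from 27% to 35%.

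**The case against.** **Section 1 is a background definition.** It rests on liver fat that this study never measures, and Section 3.5 calls its category fatty liver, not NAFLD. A surrogate may be simpler than the disease it stands for. This stands in part. But the rule keeps the alcohol exclusion, Section 1 presents liver enzymes and scores as the way to identify NAFLD, and no other NAFLD case rule exists. It is the NAFLD variable in practice, and keeping one of two stated exclusions without explanation is an inconsistency.

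**Derivation rules and drug lists belong in an analysis plan.** The drug list may. But the protocol fixes an explicit rule: a plan that followed it would inherit the gap, and one that departed from it would contradict the protocol.

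**The size is hypothetical.** This stands. No contamination rate is given, and 1.42 is a detectable effect, not an expected NAFLD effect. Section 1 cites NAFLD in 67% of overweight and up to 94% of obese people, and only these people can be labelled. Many with a second cause would have fatty liver too, which would make the dilution smaller than shown.

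Three stronger readings are tempting and not supported:

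- *That leaving out known liver disease also contradicts the protocol.* Section 1 names alcohol and drugs only.
- *That the study's main exposure is compromised.* Section 3 makes the risk model the primary outcome, with emphasis on obesity-related factors. NAFLD is one named predictor where 15 covariates are planned, and ALT, GGT, BMI, FIB-4 and the Fatty Liver Index do not pass through this label.
- *That 10%, 21% or 51% more patients would be needed.* Those figures follow from (ln 1.42/ln observed OR)² in the three cases, but they ignore the smaller exposed group that remains after the repair.

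**Conclusion.** The point holds in a limited form. The contradiction between Sections 1 and 3.5 is certain on the text and is confined to steatogenic drugs. The unused liver disease history is a worthwhile improvement of the same rule. The data are collected; it is the rule that does not use them.

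The effect on results cannot be computed from the document. Under the stated assumptions it ranges from negligible (OR 1.42 seen as 1.40, a net penalty of about 6%) to noticeable (1.33, about 30%). These figures assume 5% to 20% contamination with no adenoma effect, 20% labelled, a reference risk of 0.20 and no covariate adjustment. If the other causes relate to adenoma risk, the direction is open. Because the inconsistency is clear and the repair nearly free, it should be corrected before analysis.

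**What to change.** Reconcile Section 3.5 with Section 1 by adding to both tiers: 'and no steatogenic drug in the medication history and no other known (non-NAFLD) liver disease (questionnaire items 6 and 9)'. The non-NAFLD qualifier matters, since a recorded history of fatty liver itself must not remove a case. Fix the drug list before analysis.

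Put overweight participants who meet the ALT threshold but fail the added condition into a separate category, 'raised ALT, other cause'. They should not move to the reference group, where they would contaminate the comparison from the other side.

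The cost is one line of text, the drug list and one derived variable, with no new data or visits and nobody leaving the study. The NAFLD group becomes slightly smaller. Undiagnosed other causes stay in it, because the listed blood tests cannot find them; this should be stated as a limitation.

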#### f. Presence of advanced neoplasia

In a subset of patients attending for colonoscopy in the centres where Fibroscan is available patients will have a liver stiffness measurement by Fibroscan using the M or XL probe as appropriate.

The above data will be entered onto the CRF by a member of the research team. For patients who attend for a diagnostic colonoscopy but are taking warfarin or other anti-coagulation, polypectomy is contraindicated. If polyps are found, a further colonoscopy is usually organised as part of standard care. The polyp details will be recorded at this second colonoscopy to prevent confusion and unnecessary exclusion.

#### 4. Adverse Events

As this is an observational study, there are no expected additional adverse events specifically associated with the study. Intravenous cannula insertion may cause some discomfort and bruising.

#### 5. Assessment and Follow Up

Clinical follow up will be as per routine clinical practice. Where colonoscopy is incomplete, the reason for this will be recorded. Eligible, consented patients will remain in the study for two weeks following discharge from the endoscopy day ward on the day of their procedure. This is to allow time to collect data from the blood and histology reporting systems. No additional visits are required for patients who enter the study. Any follow up appointments post-colonoscopy will be as per routine care for the unit. The timescale for the out-patient appointment and subsequent care will be unaltered by participation in the study.

Checking liver function tests and HbA1c may pick up new diagnoses of fatty liver disease or diabetes. All abnormal blood tests will be communicated to the participant's GP for further action by a member of the research team.

#### 6. Statistics and Data Analysis

Data from the CRFs will be transferred to a secure and encrypted electronic computer database. Statistical analysis will be undertaken by [name], Professor of Biological Modelling at Newcastle University.

The relationship between adenoma incidence, NAFLD and blood markers will be investigated using logistic regression whilst adjusting for patient-related demographic variables including age and gender. This will assess the independent contribution of predictors to the odds of adenomas being found. Stepwise removal of non-significant covariates will then be used to identify variables best able to predict adenoma presence. ROC plot and AUC analyses of sensitivity and specificity will be used to characterise the ability of the model to discriminate between patients with and without adenomas and their potential as a predictive tool. These analyses assess the independent contribution of variables to the probability that adenomas will be found, but do not allow for confounding, interaction and associated indirect effects on detection. Structural Equation Modelling (SEM) will be used to investigate impact of indirect and direct effects of the predictors on adenoma incidence. Parsimonious models for logistic regression and SEM will be compared in terms of their ability to predict adenoma presence.

As multiple adenomas may occur, the extent to which adenoma number is related to abnormal liver enzymes using Poisson regression models and SEM will be measured, following the same analytical framework. It is anticipated that the presence of multiple adenomas will be zero-inflated, with some patients having zero and others many. The extent to which zero-inflated models (eg allowing for aggregation) improve the prediction of adenomas will be assessed. Robustness and validation of all models will be validated using bootstrapping. The best model will be developed into a predictive tool.

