Approximately 400,000 colonoscopies are performed each year within the NHS for the investigation of gastrointestinal symptoms, including altered bowel habit, rectal bleeding and iron deficiency anaemia. Adenoma detection rate (ADR), defined as the number of procedures in which at least one adenoma is detected, is a widely accepted quality measure. A recent colonoscopy audit demonstrated an average polyp detection rate of 32.1%; however, ADR is variable between colonoscopists. A recent study estimated mean ADR of 15.9%. Patients found to have adenomas receive surveillance procedures, however these are currently based entirely upon number and size of adenomas with no patient factors considered. The NHS Bowel Cancer Screening Programme (BCSP)

invites all individuals aged 60-74 to undertake biennial faecal occult blood testing (FOBt). Screening is currently population based and non-targeted. Patients with a positive FOBt are invited for colonoscopy. The national Bowelscope screening programme is currently being rolled out in England and Wales, with the Lead applicants unit the first nationally to deliver this programme. All individuals aged 55 are invited for a single flexible sigmoidoscopy and adenoma clearance. Those deemed to be high risk undergo completion colonoscopy.

The mean ADR per colonoscopist within the FOBt BCSP is 46.5%, which is much higher than the symptomatic population due to the targeted nature of the programme. The BCSP has demonstrated a significant stage shift in CRC diagnosed. At present, the FOBt based screening programme is not providing protection against right sided CRC. A trial within the Scottish screening programme demonstrated that screening was an effective environment for interventions to alter patient behaviour.

In summary, although a study in an Asian population suggested an association between NAFLD and colorectal neoplasia, this has not been repeated in a Western population. It is important that the association is explored in a Western population but using non-invasive markers of liver disease and a wider range of colorectal neoplasia risk factors. This will allow development of a model to predict colorectal adenoma risk guiding screening and surveillance.

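### The outcome is adenoma detection, which varies by colonoscopist, but the protocol specifies no colonoscopist code and section 6 names no operator or site level

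*Protocol*

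**What the plan says.** Section 1 (Background) treats the adenoma detection rate (ADR) as a quality measure of the procedure and says that "ADR is variable between colonoscopists". It gives the screening figure by operator as well: "The mean ADR per colonoscopist within the FOBt BCSP is 46.5" per cent.

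Section 3.1 names nine recruiting organisations (eight regional units and Kettering) and two routes in, screening and symptomatic.

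Section 3.5 itemises the questionnaire, body measurements, blood tests, lesion findings and, in a subset, Fibroscan. The lesion list opens with "Following colonoscopy to allow completion of the histological dataset, additional information will be collected" and covers cancers and adenoma features; the word site there means the site of the lesion. No colonoscopist code and no examination-quality item such as bowel preparation appears. Section 3.1 also says that data from the procedure will go onto the case report form, without listing them.

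Section 6 describes the logistic model thus: "This will assess the independent contribution of predictors to the odds of adenomas being found", "whilst adjusting for patient-related demographic variables including age and gender". It concedes that these analyses "do not allow for confounding, interaction and associated indirect effects on detection". The remedy offered is that "Structural Equation Modelling (SEM) will be used to investigate impact of indirect and direct effects of the predictors on adenoma incidence". On validation it says: "Robustness and validation of all models will be validated using bootstrapping". None of the logistic, count, structural equation or bootstrap steps names colonoscopist, recruiting site or clustering.

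**The concern.** An adenoma that is found reflects both the patient's risk and the examination. The protocol names the operator as a source of variation in its own outcome, then specifies neither its collection nor its modelling. The structural equation step does not fill the gap, since it concerns the predictors and has no operator or site level.

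Three things are at stake.

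- **Confounding.** If patients with abnormal liver enzymes or obesity are seen more often by operators who find more (or fewer) adenomas, part of the operator difference is credited to the patient factor.
- **Calibration.** The end product is a predictive tool meant to inform screening. If a new unit's detection differs from the study mix, predicted risks there will be too high or too low. A bootstrap that resamples patients, the usual default when no unit is named, draws on the same operators and sites each time and cannot show this.
- **Counts.** Differences in detection between operators can look like the aggregation of adenomas that the zero-inflated models are meant to describe in patients.

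**Working it through.** **The plan's own figures (section 3.1).** The rule is N = 10k/p with k = 15.

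- Symptomatic: 10 × 15 / 0.15 = 1000.
- Screening: 10 × 15 / 0.35 = 428.6, stated as 430.
- Total 1430, as stated. Expected adenoma prevalence is (0.15 × 1000 + 0.35 × 430) / 1430 = 300.5 / 1430 = 21%.

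These reproduce and are not in dispute.

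**Size of an operator effect (assumption).** The documents give no spread. Suppose 95% of operators lie between ADR 8% and 25%.

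- logit(0.08) = −2.44 and logit(0.25) = −1.10, so SD = 1.34 / 3.92 = 0.34.
- For a patient at 15% (logit −1.73), one SD lower gives −2.07, or about 11%; one SD higher gives −1.39, or about 20%.

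That is the possible calibration shift between operators. The ratio 25 / 8, about three, only restates the assumed range and is not evidence.

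**Type I error for a patient factor with no true effect (simulation, N = 1430).**

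| Setting (all assumed) | Type I error without operator or site term |
|---|---|
| Nine sites, outcome SD 0.35, exposure SD between sites 0.25 | 5.0% and 5.9% in two runs |
| Same, exposure SD 0.5 | 6.9% and 6.2% in two runs |
| Operators nested in sites, exposure SD 0.5, one operator per site | 6.4% |
| Same, three or five operators per site | 5.5% |
| 50 operators, SD 0.3 to 0.5, exposure unrelated to detection | 5.3% to 5.0% (mean OR 1.00 to 0.99) |
| Same, operator-level correlation 0.5 | 9% to 12% (mean OR 1.08 to 1.11) |
| Same, correlation 1.0 | 19% to 34% (mean OR 1.15 to 1.24) |

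The first two rows used 1500 datasets per run, so the Monte Carlo standard error is about √(0.05 × 0.95 / 1500) = 0.6 percentage points. With site indicators in the model, error in those two rows was about 5%. The last row is a limiting case, not an expectation.

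**Dilution.** With exposure unrelated to operator and a true OR of 1.42, omitting an operator effect of SD 0.3 to 0.5 gave a mean OR of about 1.39 to 1.40.

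**Discrimination.** With 45 operators, SD 0.35 and patient mix unrelated to operator, AUC was 0.694 with the same operators and 0.694 with new ones.

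**Cost of each remedy under the plan's own rule.**

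- Eight site indicators: k = 15 + 8 = 23, so 10 × 23 / 0.15 + 10 × 23 / 0.35 = 1533 + 657 = about 2190, above the cap of 2000.
- One random intercept, counted as one parameter: k = 16, so 1067 + 457 = about 1524, below the cap.

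**The case against.** The strongest reply is that nothing shows the colonoscopist code will go uncollected. The list in section 3.5 completes the histological data, and the procedure data mentioned in section 3.1 are not itemised, so the code may be on the case report form. If it is not, it could probably be retrieved: section 3.5 already draws on hospital reporting systems and the screening dataset, and section 8.2 keeps source documents for fifteen years. Recruiting site is probably recoverable too. Random effects and clustered validation are often left to a statistical analysis plan, and the adjustment set in section 6 is not presented as exhaustive. Nor is examination quality ignored: incomplete procedures are a withdrawal criterion and the reason is recorded.

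Most of this stands, and it limits the point. A reader might infer that the operator code is lost for good; the protocol shows only that it is not specified. A reader might infer that the liver odds ratios are confounded; that needs patient mix to differ by operator or site, which is plausible across nine units and two pathways but not shown. A reader might also infer that the bootstrapped AUC must be too high; the simulation above, with unrelated patient mix, gives no support for that.

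What does not fall is the gap itself. Data items belong in a protocol, section 3.5 sets them out in detail, and a determinant of the outcome that the background names is not among them. Completeness of the procedure does not measure how well adenomas were looked for.

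**Conclusion.** The point holds in a limited form. The outcome is detection, the protocol says that detection varies by colonoscopist, and it neither specifies the items needed to account for this nor names an operator or site level in the models or the validation. Operator and site differences can appear as patient risk where patient mix differs; otherwise they add unexplained variation.

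The main consequence is that calibration in new units goes unassessed. Under the assumed operator SD of 0.34, a 15% risk becomes about 11% or 20% with operators one SD away. The expected effect on type I error is small, about 5% to 7%, rising only if exposure tracks operator detection. Every one of these sizes rests on an assumed operator spread. The study would remain interpretable as an association study; it is the tool's use elsewhere that lacks support. The change is worth making because it is cheap, and easier before data collection than after.

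**What to change.** **Section 3.5.** List a pseudonymised colonoscopist code, the recruiting site and bowel-preparation quality among the procedure items on the case report form, taken from the routine endoscopy report.

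**Section 6.**

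- Fit the logistic and count models with a random intercept for colonoscopist and/or site, or use cluster-robust errors, and keep these out of the stepwise removal. Robust errors correct the standard errors only, so the random intercept is preferable where patient mix may differ by operator.
- Do not use site fixed effects. They take the 10k/p rule to about 2190, above the cap, and give no coefficient for a new unit.
- Base the tool's predictions on the patient terms.
- Resample by cluster in the bootstrap.
- Report leave-one-site-out AUC and calibration.

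**Cost.** Three fields and a few lines of analysis wording. Intervals will be slightly wider and validated performance may look less favourable. Counting the random intercept as one parameter moves the rule from about 1430 to about 1524, within the cap. With only nine units, a site-level variance will be imprecise, which favours colonoscopist as the cluster where the code is available.
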